#### 5.5.2.1 Definitions

- **Adverse Event (AE)** : An *AE* is any undesirable clinical event occurring to a patient, during a clinical trial, whether or not it is considered related to the device. This includes a change in a patient's condition or laboratory results which has or could have a deleterious effect on the patient's health or well-being.
- **Adverse Device Effect (ADE)**: An adverse device effect related to registry device(s).
- **Serious Adverse Event (SAE)**: A *SAE* is an event that:
  - a. Led to death
  - b. Led to a serious deterioration in the health of the patient that:
    - Resulted in life-threatening illness or injury
    - Resulted in permanent impairment of a body structure or a body function
    - Required in-patient hospitalization or prolongation of existing hospitalization
    - Resulted in medical or surgical intervention to arrest permanent impairment to body structure or a body function
    - Led to fetal distress, fetal death or a congenital abnormality or birth defect
- **Unanticipated Adverse Device Event (UADE)**: An event that has an Adverse Device Effect, the specificity or severity of which is

not consistent with the risk information described in the *Instruction for Use* or the clinical protocol.

### 5.5.2.2 Relationship to the Registry Device

An AE is considered to be device-related when it is reasonable to believe that the event may have been caused by or is related to the device. Following definitions will be used to assess the relationship of the adverse event to the use of registry device. Any grading for relatedness other than 'unrelated' will be considered device related.

- **Definite:** The temporal sequence is relevant and the event abates upon device application completion/removal, or reappearance of the event on repeat device application
- **Probable:** The temporal sequence is relevant or the AE abates upon device application completion/removal or the AE cannot be reasonably explained by the subject's condition or comorbidities. The AE is related or most likely associated with the device
- **Possible:** The temporal sequence between the device and the AE is such that the relationship is not unlikely or there is no contradicting evidence that can reasonably explain the registry subject's condition. There is a possibility of a relationship between the AE and the device
- **Unrelated:** The AE is not associated with the device. There is no relation between the AE and the device

Similar grading will be used for assessing the relationship to procedure.

### 5.5.2.3 Adverse Event Severity

For the purposes of this trial, the investigator will use the following definitions to rate the severity of each adverse event.

- **Mild:** Awareness of a sign or symptom that does not interfere with the patient's usual activity or is transient, resolves without treatment and with no sequelae
- **Moderate:** interferes with routine activity and/or requires symptomatic therapy
- **Severe:** Severe discomfort and significant impact on the subject's ability to perform routine activities despite symptomatic therapy

Minimum requirements of data to be recorded are: type of event, duration of event (start through end), severity, seriousness, action taken, outcome and, if appropriate, causality.

The Investigator is required to report any device or procedure related AE, UADE and/or SAEs to the Sponsor or its designee as soon as possible, but no later than 24 hours after the event is known. All serious adverse events or serious device effects must document an explanation of any medical treatment administered. The form must be completed and submitted to the Sponsor or its designee within five working days.

An event need not be reported as a SAE if it represents only a relapse or an expected change or progression of the condition that was the cause of treatment without any other symptoms and signs than those present before treatment. This type of event is considered an AE, and may not be reportable.

When appropriate, the IRB/EC shall be informed by the investigator about serious adverse events and adverse device effects associated with the use of the product, and Penumbra is responsible for informing the Health Authorities and other investigators of such events as appropriate.

## 5.6 Withdrawal of Approval

The investigator shall report to Penumbra immediately if, for any reason, the approval to conduct the investigation is withdrawn by the IRB/EC. The report will include a complete description of the reason(s) for which approval was withdrawn. The investigator shall submit all reports in a timely manner.

## 5.7 Records Retention

The investigator shall maintain the records associated with this registry for a period of at least two years after the date on which the investigation is completed. These records include the following:

- Correspondence with the Sponsor or designee, the medical monitor, and other investigators.
- Patient records, including informed consent forms, copies of all completed eCRFs, and supporting documents.
- Current registry protocol with dates and details of reasons for any deviations from the protocol that could affect the scientific quality of the registry or the rights, safety, or welfare of the patients.
- Reports of any serious adverse event or adverse device effects.
- A copy of all approvals related to the clinical investigation.
- The approved, blank, informed consent form.
- Certification that the investigational plan has been approved by the IRB/EC.
- Signed investigator agreements and current signed and dated *curriculum vitae* of the registry investigator and all participating investigators.

## 6. SPONSOR RESPONSIBILITIES

### 6.1 Training

During registry initiation, the Sponsor will train the investigator and registry staff on the protocol as well as the eCRFs.

### 6.2 Investigator List

The Sponsor shall keep a list of the names, addresses, and professional positions of the investigators for the registry.

### 6.3 Adverse Event Reporting

The Sponsor shall evaluate adverse event reports received from the registry sites and those found during data monitoring and shall report them to the regulatory bodies and other investigational sites as appropriate.

### 6.4 Data Monitoring

Sponsor will be utilizing both centralized and on-site monitoring during the trial. Standardized eCRFs will be used for queries and query resolution. A Penumbra employee or designate will conduct the following site visits:

#### 6.4.1 Site Initiation Visit

This is conducted on site or remotely to train the registry staff on registry requirements, and other relevant training.

#### 6.4.2 Interim Monitoring Visit

Conducted as needed to ensure the registry site is operating in compliance with this protocol, and completing the eCRFs. Clinical monitoring will include review and resolution of missing or inconsistent data and source document checks to ensure the accuracy of the reported data. eCRFs for all enrolled patients will be made available to the Sponsor for review as agreed with the investigator. The Sponsor will evaluate and summarize the results of each site visit in written reports, identifying repeated data problems with any investigator and specifying recommendations for resolution of noted deficiencies. To facilitate this monitoring, certain source documents may be requested. These may include, but are not limited to, patient informed consent, history and physical, operative report, imaging reports, and discharge summary.

#### **6.4.3 Registry Close-Out Visit**

This visit is conducted at the termination of the registry to resolve any outstanding data queries and reconcile trial documents.

#### **6.5 Data Management**

All registry data will be entered into an electronic data capture (EDC) system provided by a vendor. Registry personnel will have individual login and password to access the clinical registry information based upon each individual's roles and responsibilities. For data security, the system operates within the Secure Socket Layer (SSL) 256-bit encryption protocol. This application is designed to support compliance with the appropriate regulations and guidance for industry.

Data entry will be performed at the investigational sites. Standardized eCRFs will be provided for use at all investigational sites. Investigators are responsible for completion and timely submission of the data to Penumbra, Inc. This EDC system requires no on-site software installation or specific hardware to operate.

Investigators, clinical coordinators, data managers, and Penumbra clinical personnel access project information and registry data centrally via a Web browser. Incoming data are to be reviewed for quality and consistency before being locked for data export. Questions or problems with submitted data will be addressed with the principal investigator or designee via an electronic querying system, or through direct contact.

All hard copy forms and data files will be secured to ensure confidentiality. Investigators are required to maintain source documents required by the protocol, including laboratory results, patient report forms, supporting medical records, and Informed Consent Forms. The source documents will be used during the regular monitoring visits to verify information submitted on the eCRFs.

## 8. ETHICAL REQUIREMENTS

### 8.1 IRB/EC Approval

The investigator is responsible for ensuring that the registry is conducted according to any conditions imposed by the reviewing Institutional Review Board (IRB) or Ethics Committee (EC), and all other applicable regulations. It is the responsibility of the investigator to obtain approval of the registry protocol from the IRB/EC and to keep the IRB/EC informed of any unexpected serious adverse events, serious adverse device effects, and amendments to the protocol, as applicable. All correspondence with the IRB/EC should be filed by the investigator and copies sent to the Sponsor or its designee.

### 8.2 Patient Information and Consent

It is the responsibility of the investigator to give each patient full and adequate verbal and written information regarding the objective and procedure of the registry and the possible risks involved and to obtain signed informed consent from all patients prior to inclusion in the registry unless the patient's health condition does not allow informed consent, in which case the state and national procedures will be applied. For patients being treated in emergent cases (i.e. ruptured aneurysm), patients will be allowed to be enrolled if they sign consent no longer than 1 calendar day after the procedure or if a legally authorized representative signs the informed consent form on the patient's behalf. The original, signed consent is filed with the patient registry records, and a copy is provided to the patient or legally authorized representative.

### 8.3 Patient Data Protection

The patients will be identified in the eCRFs with a unique patient identifier. Only the investigator will have access to individual patient data, as will the Sponsor or its designee for monitoring purposes only. Furthermore, the patients should be informed about the possibility of inspection of relevant parts of the hospital records, including angiograms and other imaging scans, by the Sponsor or other health authorities, including the FDA.

## 9. STATISTICAL PROCEDURES

### 9.1 Sample Size Justification

Approximately 1,000 patients will be enrolled in this post market registry. Assuming an observed rate of 8.3% for the endpoint of re-treatment at follow-up, the sample size precision is greater than  $\pm 2\%$  for this endpoint (95% CI: 6.6% to 10.0%). Assuming an observed rate of 1.7% for the primary endpoint of procedural device-related serious adverse events at immediate post-procedure

(data on file at sponsor), the sample size precision is greater than  $\pm 1\%$  for this endpoint (95% CI: 0.93% to 2.5%). These precision estimates are based on binomial 95% confidence intervals. Hence, the sample size provides an adequate level of precision for these primary endpoints.

## 9.2 General Statistical Methods

This registry is a single-treatment design. Hence, descriptive statistics will provide a basis for the majority of the analyses with a 95% two-sided confidence interval presented. For binary outcomes, the 95% two-sided confidence intervals will be calculated using binomial intervals. For numeric measures, a confidence bound for the mean or mean change from admission will be constructed.

Summary tables (descriptive statistics and/or frequency tables) will be provided for all baseline variables, effectiveness variables, and safety variables, as appropriate. Continuous variables will be summarized with descriptive statistics (n, mean, standard deviation, range, and median). Frequency counts and percentage of patients within each category will be provided for categorical data.

Results collected at multiple visits will be summarized at each visit for which they are collected. Summaries for all measures will include all observed data for each visit.

## 9.3 Safety

Tabulations of adverse events will be presented with descriptive statistics at immediate post procedure and follow-up visits. Adverse event incidence rates will be summarized by category and seriousness of the adverse event. Events will also be reported by relationship to the device.

# 10. PUBLICATION OF INFORMATION

The results of this registry may be offered for publication and/or presentation. The investigators and the Sponsor shall collaborate in the writing of the registry to ensure accuracy. The investigator agrees to use this data only in connection with this registry and will not use it for other purposes without written permission from the Sponsor.

## 1 Overview

SMART is a multicenter, single-arm prospective registry. Its primary objective is to acquire postmarket data on the use of the Penumbra SMART COIL® System (Smart) in the treatment of intracranial aneurysms and other malformations.

Approximately 1,000 subjects with intracranial aneurysms or other malformations treated by Smart will be enrolled across up to 100 sites. All subjects will be allocated to treatment with at least 75% Smart, Penumbra Coil 400™ (PC 400), or Penumbra Occlusion Device (POD®) coils as defined by the number of coils implanted.

The primary efficacy endpoint is the rate of retreatment through one year  $\pm$  6 months follow-up. The primary safety endpoint is the rate of procedural (within 24 hours of arterial puncture) device-related serious adverse events.

The secondary efficacy endpoints for the registry are the ability to achieve adequate occlusion at immediate post-procedure (Class I or II Raymond-Roy Occlusion Classification for aneurysms) and the number of times re-access with guidewire was required due to catheter kickout while using SMART/POD/PC 400.

This Statistical Analysis Plan (SAP) elaborates on statistical methods outlined in the registry protocol and presents analysis conventions. The SAP will be signed off before database lock.

## 2 Sample Size

The predetermined sample size of approximately  $n = 1000$  subjects allows the primary efficacy and safety endpoints to be estimated with greater than  $\pm 2\%$  precision: re-treatment at one-year follow-up (95% CI: 6.6% to 10.0%) and procedural device-related serious adverse events (95% CI: 0.93% to 2.5%).

This analysis applies 95% two-sided binomial proportion confidence intervals using normal approximations to the binomial (SAS v 9.4; SAS Institute, Cary, NC).

These estimates assume 8.3% retreatment through one-year follow-up based on the mean rate observed in eight prior studies cited in the protocol, as weighted by their subject sample sizes. A 1.7% rate of procedural device-related serious adverse events is assumed based on data on file at the sponsor.

## 3 Interim Analysis

No interim efficacy analyses are planned for the purpose of terminating the registry early. However, interim analysis may be performed for the purpose of publication of SMART results.

## 4 Analysis Populations

### 4.1 Definitions

The ITT population will consist of all subjects who sign the informed consent and are enrolled in the registry with Smart, PC 400, or POD accounting for 75% or more of the total number of coils implanted. The ITT population will include only the first lesion treated for each subject. Summary statistics will be developed separately for additional lesions.

The PP population will be constructed by excluding subjects who have major protocol violations that impact endpoint evaluations. Subjects will be classified as screen failures if they are not consented or are consented and not enrolled due to failure to implant at least 75% Smart, PC 400, or POD coils or other reasons.

## 5 Statistical Methods

For this single-arm registry, results will primarily be presented as descriptive statistics and two-sided 95% confidence intervals.

Baseline, efficacy, and safety variables will be summarized using tables of descriptive statistics for continuous variables (n, mean, median, SD, and range) or frequency counts and percentages for categorical variables.

Confidence intervals will be developed using confidence bounds on the mean or mean change from admission for continuous variables or binomial proportion intervals under a normal approximation to the binomial for categorical variables.

For results developed using data from more than one visit, summaries will be reported for each visit from the full set of observed data available.

Staged procedures are not retreatments for the purposes of running all SMART registry analyses.

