## 6 Baseline Characteristics

Baseline characteristics will be summarized using descriptive statistics for continuous variables or frequency counts and percentages for categorical variables. Two-sided 95% confidence intervals will also be presented.

A summary table will be reported with key baseline characteristics, including subject demographics, admission functional assessments, and lesion evaluation results.

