## 8 Effectiveness Analysis

### 8.1 Primary Effectiveness Analysis

The primary efficacy outcome is the rate of retreatment through one-year follow-up. Frequency counts and percentages will be reported for the subjects who required retreatment. A two-sided 95% binomial proportion confidence interval will be developed for the retreatment rate using a normal approximation to the binomial. All primary and secondary efficacy endpoint analyses will be run on both the intent-to-treat (ITT) population and the per-protocol (PP) population.

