### 8.2 Secondary Effectiveness Analysis

Frequency counts and percentages will be reported for the two secondary efficacy outcomes:

- **Ability to achieve adequate occlusion at immediate post-procedure:** Defined as the proportion of subjects achieving adequate occlusion based on the investigator's assessment given anatomical and other considerations at immediate post-procedure.

This endpoint applies to the investigator's Yes/No assessment on whether adequate occlusion was achieved and not the Raymond-Roy Occlusion Scale. Frequency counts and percentages will be reported for this proportion. Two-sided 95% binomial proportion confidence intervals will be developed, using a normal approximation to the binomial.

- **Re-access with guidewire due to catheter kickout:** This endpoint applies to catheter kickout while using SMART/PC 400/POD coils and not other adjunctive coils. Frequency counts and percentages will be reported for the proportion of subjects experiencing 0, 1, 2, and  $\geq 3$  kickout events. Two-sided 95% binomial confidence intervals with a normal approximation to the binomial will be presented for each frequency count.

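### The SAP uses Wald intervals for every proportion and has no rule for zero or sparse counts: little effect on the primary endpoints at n = 1,000, but degenerate or too-short intervals in sparse cells

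*SAP*

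**What the plan says.** SAP 5 sets the general rule: "binomial proportion intervals under a normal approximation to the binomial for categorical variables". SAP 8.1 repeats it for the primary effectiveness endpoint ("A two-sided 95% binomial proportion confidence interval will be developed for the retreatment rate using a normal approximation to the binomial"). SAP 8.2 does so for adequate occlusion and for the kickout categories ("Two-sided 95% binomial confidence intervals with a normal approximation to the binomial will be presented for each frequency count"), SAP 10.1 for the primary safety endpoint, and SAP 10.3 for one-year mortality. The planning calculation in SAP 2 is on the same footing: "This analysis applies 95% two-sided binomial proportion confidence intervals using normal approximations to the binomial".

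Protocol 9.2 is less specific: "For binary outcomes, the 95% two-sided confidence intervals will be calculated using binomial intervals". The SAP therefore narrows the protocol and does not contradict it.

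Intervals are wanted widely. On baseline variables SAP 6 says "Two-sided 95% confidence intervals will also be presented", and the Appendix shells carry a 95% CI column beside rows such as fibromuscular dysplasia (Medical History) and three or more kickouts (Secondary Effectiveness Analysis). SAP 14 requires every category to be listed, including empty ones, but gives only a print format for them. Neither document gives an interval rule for 0/N, N/N or low counts.

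For subgroups, SAP 9 names tests only. The subgroup shell has CI columns, so Wald intervals there follow from SAP 5. SAP 9 includes the safety endpoints, but the shell has no safety row and SAP 14 refers to the section by a title limited to effectiveness. Safety intervals by subgroup are therefore an inference.

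**The concern.** The Wald interval takes its standard error from the observed proportion. When few events are seen, the standard error is too small as well as the estimate, and at zero events it vanishes. The interval then fails in one direction: its upper limit is too low.

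This registry tests no hypothesis on its main endpoints, so the interval is its principal inferential output. For uncommon harms the upper limit is the figure a reader will use, and that is the limit that is understated. A printed 0.0% to 0.0% claims certainty, and a negative lower limit is not a possible rate.

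**Working it through.** **Inputs.** From Protocol 9.1 and SAP 2: n of about 1,000, retreatment 8.3%, procedural device-related serious adverse events 1.7%. From SAP 5: two-sided 95%, so z = 1.96. Assumed, because the documents give no subgroup sizes or category frequencies: groups of 50 to 500, rates of 1% to 3% in groups, and 0.1% to 0.5% for rare rows in the full cohort.

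**1. The plan's own figures.** Wald: p ± 1.96 × √(p(1 − p)/n).

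- Retreatment: 1.96 × √(0.083 × 0.917/1000) = 1.71 points, giving 6.59% to 10.01%. The printed 6.6% to 10.0% reproduces. Exact (Clopper-Pearson) gives 6.67% to 10.19%.
- Serious adverse events: 1.96 × √(0.017 × 0.983/1000) = 0.80 points, giving 0.90% to 2.50%. The printed upper limit of 2.5% reproduces; the printed lower limit of 0.93% does not. Nor is it given by continuity-corrected Wald (0.85% to 2.55%), Wilson (1.06% to 2.71%), exact (0.99% to 2.71%), Agresti-Coull (1.04% to 2.73%) or Jeffreys (1.03% to 2.65%).

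**2. Zero and low counts.** With x = 0 the standard error is 0, so the interval is 0.0% to 0.0%. The exact upper limit is 1 − 0.025^(1/n). By symmetry N/N gives 100% to 100%. The Wald lower limit is negative when x < 3.84 × (1 − x/n), which holds for x = 1, 2 and 3 at any n of 14 or more.

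| Count | Wald (%) | Exact (%) |
|---|---|---|
| 0/50 | 0 to 0 | 0 to 7.11 |
| 1/100 | −0.95 to 2.95 | 0.03 to 5.45 |
| 0/1000 | 0 to 0 | 0 to 0.37 |
| 1/1000 | −0.10 to 0.30 | 0.00 to 0.56 |

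**3. Coverage.** For a true rate p, sum the binomial probabilities of all counts whose interval contains p. Wald, in percent:

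| True rate | n | Covered | Upper limit below truth | Lower limit above truth |
|---|---|---|---|---|
| 1.7% | 50 | 57.6 | 42.4 | 0.0 |
| 1.7% | 100 | 81.8 | 18.0 | 0.2 |
| 1.7% | 200 | 85.3 | 14.5 | 0.2 |
| 1.7% | 500 | 92.1 | 7.3 | 0.6 |
| 1.7% | 1000 | 94.4 | 4.8 | 0.8 |
| 8.3% | 50 | 92.0 | 7.3 | 0.7 |
| 8.3% | 100 | 91.7 | 7.5 | 0.8 |
| 8.3% | 1000 | 94.6 | 3.5 | 1.9 |

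The first two rows can be checked by hand: the upper misses are the samples with no event, 0.983^50 = 42.4% and 0.983^100 = 18.0%. At 1.7% and n = 1,000, exact and Wilson both give 96.4 / 1.2 / 2.4.

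**4. Range over assumed rates.** Coverage (%) over true rates of 1% to 3%:

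| n | Wald | Share of rates with Wald below 90% | Exact | Wilson |
|---|---|---|---|---|
| 50 | 39.5–78.1 | 100% | 97.5–99.6 | 89.5–98.2 |
| 100 | 63.3–94.7 | 67% | 97.5–99.5 | 91.6–98.0 |
| 200 | 79.3–94.9 | 49% | 95.1–99.3 | 93.0–97.8 |
| 500 | 87.1–95.2 | 10% | 95.2–98.5 | 93.5–97.3 |
| 1000 | 90.6–95.4 | 0% | 95.05–97.6 | 93.8–96.6 |

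For rare rows in the full cohort (n = 1,000, rates of 0.1% to 0.5%): Wald 63.2–94.8, exact 95.9–99.5, Wilson 91.6–98.0.

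**5. The 3% threshold in SAP 10.2.** At n = 1,000 this is 30 subjects, where Wald (1.94% to 4.06%) and exact (2.03% to 4.26%) are close. It removes many sparse adverse-event categories. It does not reach kickout cells, baseline rows, subgroup levels, deaths or the primary safety endpoint.

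**The case against.** The registry is descriptive, no performance goal or stopping rule rests on an interval, and n/N stands in each cell, so a reader can recompute. At n = 1,000 the primary limits move by about 0.2 points. The worst coverage figures are for a rate of about 1.7% within strata, a table that the subgroup shell does not show; retreatment, which it does show, stays near 92% at n = 50. Subgroup comparisons of the binary endpoints use Fisher's exact test and do not depend on these intervals. The sparse rates are assumed, and over the assumed range some rare cells are close to nominal.

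Most of this stands as a limit on weight. It keeps the severity low and makes the stratum figures for safety conditional on such intervals being produced. It does not remove the defect. An exact p-value does not repair a 0.0% to 0.0% interval printed beside it. The failures at zero to three events need no assumed rate, only that such a count occurs, and SAP 14 already provides for empty categories.

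A narrower remedy, exact intervals for low counts only, would leave the planning figures alone. But it needs a threshold, mixes two methods in one table, and leaves 4.8% of upper limits below the true rate on the primary safety endpoint.

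**Conclusion.** The point holds, at low severity. Followed as written, the plan prints degenerate intervals at 0/N and impossible lower limits at one to three events. For the primary endpoints at the planned size and rates the effect is slight: coverage is within about 0.6 points of nominal, although for safety 4.8% of upper limits fall below the true rate, against a nominal 2.5%. In sparse cells it can be large: 57.6% to 85.3% coverage at 1.7% for n = 50 to 200, and as low as 63% for a row at 0.1% to 0.5% in the full cohort. Those last figures depend on assumed sizes and rates. There is no conflict with the protocol, which leaves the method open.

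**What to change.** In SAP 5, 8.1, 8.2, 10.1 and 10.3, replace the normal approximation with one named method. Clopper-Pearson is the safer choice: it keeps at least 95% coverage and handles 0/N and N/N without a special rule. Wilson is a reasonable alternative with shorter intervals, but its coverage dips to 89.5% at n = 50, so the choice should be made and written down now. Add a sentence to SAP 9 that any subgroup interval uses the same method.

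Restate the planning intervals in SAP 2 and Protocol 9.1. By the exact method they are 6.7% to 10.2% for retreatment and 0.99% to 2.71% for serious adverse events; this also replaces the 0.93% that does not reproduce. The precision statements in Protocol 9.1 and the synopsis need a matching check. For retreatment ±2% still holds on both sides (upper arm 10.19 − 8.3 = 1.89 points). For safety the upper arm is 2.71 − 1.7 = 1.01 points, so ±1% holds only for the half-width, (2.71 − 0.99)/2 = 0.86 points, and should be worded that way.

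The cost is SAP wording, a programming option and the restated figures. Exact intervals are conservative, hence somewhat wide in small groups (97.5% to 99.6% coverage at n = 50). SAP 1 places sign-off before database lock and SAP 13 allows a revised SAP, so there is a route for the change.

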## **11 Pooling Across Centers**

To assess the validity of data pooling, heterogeneity across sites will be examined using relevant methods, such as ANOVA (continuous variables), contingency tables or binary logistic regression (categorical variables), or Cox proportional hazards (event time variables). Any sites containing fewer than ten subjects will be aggregated in this analysis.

All sites will conduct the registry according to a common protocol. Monitoring efforts will be allocated to assess whether sites are adhering to the protocol in a standardized manner to minimize the presence of heterogeneity across centers.

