### Pooling Across Centers

| Pooling Across Centers | Adjunctive Treatment Used (Yes/No) | Age ≥ 65   | Aneurysm Location: ICA | Aneurysm Size: Small | Aneurysm Status: Ruptured | Lesion Nature: Aneurysm | Lesion Treatment Technique: Deconstructive | Neck Width: Wide neck | Vessel Treatment at Admission: Retreatment |
|------------------------|------------------------------------|------------|------------------------|----------------------|---------------------------|-------------------------|--|-----------------------|--|
| 99999                  | X.X% (n/N)                         | X.X% (n/N) | X.X% (n/N)             | X.X% (n/N)           | X.X% (n/N)                | X.X% (n/N)              | X.X% (n/N)                                 | X.X% (n/N)            | X.X% (n/N)                                 |
| 99999                  | X.X% (n/N)                         | X.X% (n/N) | X.X% (n/N)             | X.X% (n/N)           | X.X% (n/N)                | X.X% (n/N)              | X.X% (n/N)                                 | X.X% (n/N)            | X.X% (n/N)                                 |
| ...                    |                                    |            |                        |                      |                           |                         |  |                       |  |
| P-value                | X.XXX                              | X.XXX      | X.XXX                  | XXXX                 | X.XXX                     | X.XXX                   | X.XXX                                      | X.XXX                 | X.XXX                                      |

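### The primary-endpoint intervals and the ±2% precision assume independent subjects across up to 100 sites, and the pooling check names no endpoint, so between-site variation in outcomes is left out of the error bars

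*SAP*

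**What the plan says.** SAP 1 sets the scale: "Approximately 1,000 subjects with intracranial aneurysms or other malformations treated by Smart will be enrolled across up to 100 sites".

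For precision, SAP 2 says that this sample size "allows the primary efficacy and safety endpoints to be estimated with greater than" ±2% precision. Its method is explicit: "This analysis applies 95% two-sided binomial proportion confidence intervals using normal approximations to the binomial". For procedural device-related serious adverse events (SAEs), Protocol 1 and 9.1 claim the tighter ±1%.

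For the analysis, the general rule in SAP 5 is "binomial proportion intervals under a normal approximation to the binomial for categorical variables". SAP 8.1 (retreatment), 8.2 (occlusion and kickout), 10.1 (procedural SAE) and 10.3 (one-year mortality) repeat it. Neither document mentions an ICC, a design effect, a cluster-robust variance or a site effect in any interval.

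SAP 11 plans to examine heterogeneity across sites in order to judge whether pooling is valid. It offers ANOVA, contingency tables or logistic regression, and Cox models as example methods. It names no variable, sets no threshold and states no consequence. The mock table in the SAP Appendix has nine columns, beginning with "Adjunctive Treatment Used (Yes/No)". All nine describe case mix or treatment choice: adjunct use, age, location, size, rupture status, lesion nature, technique, neck width and prior treatment. There is no column for retreatment, occlusion, kickout or SAEs.

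**The concern.** A simple binomial interval is right when subjects are independent. Here there are concrete reasons to expect outcomes to be correlated within a site:

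- Protocol 3.1 and the schedule of assessments leave data collection and the single follow-up visit to local practice, within one year ±6 months.
- SAP 10.2 takes adverse events as the sites assess them, so device-relatedness, which helps define the primary safety endpoint, is a local judgement.

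If outcome rates differ between sites, the binomial interval is too narrow for a statement about the device beyond the participating sites. Intervals are the main inferential output of this single-arm registry. The SAP sees that pooling needs support, but the output it specifies cannot show whether outcome rates differ by site, and no result of the check would alter an interval.

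**Working it through.** **Inputs from the documents.** n = 1,000 and up to 100 sites (SAP 1), so the average is at least 10 per site. "These estimates assume 8.3% retreatment through one-year follow-up" and "A 1.7% rate of procedural device-related serious adverse events is assumed" (both SAP 2). Confidence level 95%, two-sided, normal approximation.

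**Assumed inputs.** ICC of 0.01, 0.02 and 0.05; 100 or 50 equal sites, or 100 sites whose sizes have a coefficient of variation (CV) of 1. None of these is in the documents.

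**Step 1: reproduce the plan's figures.**

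- Retreatment: 1.96 × √(0.083 × 0.917 / 1000) = 1.71 points, so 6.59% to 10.01%. This matches the SAP's 6.6% to 10.0%.
- Procedural SAE: 1.96 × √(0.017 × 0.983 / 1000) = 0.80 points, so 0.90% to 2.50%. The upper limit matches. The SAP prints 0.93% for the lower limit, a small separate discrepancy that does not bear on this point.

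The stated precision is therefore the independence calculation, with nothing added for sites.

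**Step 2: add a design effect.** DE = 1 + [m(1 + CV²) − 1] × ICC, with m = 1000 / number of sites. The half-width is multiplied by √DE.

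- 100 equal sites: m = 10, so DE = 1 + 9 × ICC.
- 50 equal sites: m = 20, so DE = 1 + 19 × ICC.
- 100 sites with CV 1: 10 × 2 − 1 = 19, the same DE as 50 equal sites.

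| Assumed ICC | Retreatment, 100 equal sites: DE, half-width | Retreatment, 50 equal sites or 100 with CV 1: DE, half-width |
|---|---|---|
| 0 | 1.00, ±1.71 | 1.00, ±1.71 |
| 0.01 | 1.09, ±1.79 | 1.19, ±1.87 |
| 0.02 | 1.18, ±1.86 | 1.38, ±2.01 |
| 0.05 | 1.45, ±2.06 | 1.95, ±2.39 |

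**Step 3: where ±2% stops holding.** The limit is DE = (2.00 / 1.71)² = 1.37, an effective sample of about 731. That gives ICC = 0.368 / 9 = 0.041 with 100 equal sites, and 0.368 / 19 = 0.019 with 50 equal sites or CV 1.

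**Step 4: coverage of the nominal 95% interval**, 2Φ(1.96 / √DE) − 1. At ICC 0.01, 0.02 and 0.05 it is 94.0%, 92.9% and 89.6% with 100 equal sites, and 92.8%, 90.5% and 84.0% in the other two layouts.

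**Step 5: procedural SAE.** At ICC 0.05 with 100 equal sites, 0.80 × √1.45 gives ±0.96, still within ±1%. With 50 equal sites or CV 1 it is ±1.12. The ±1% limit is reached at DE = (1.00 / 0.80)² = 1.56 (1.558 unrounded), that is, ICC 0.062 or 0.029 respectively.

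**The case against.** The best counter-argument is that little depends on this. The registry is descriptive, with no performance goal, no primary hypothesis test and no early-stopping rule (SAP 3 and 5). No decision turns on 1.7 against 1.9 points. For a statement only about patients at these sites, with the sites taken as fixed, between-site variation does not widen the interval. This stands as a reason to rate the point low. It does not remove the point, because Protocol 3 presents the registry as real-world experience with the device, which readers will carry beyond the enrolled sites.

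Three stronger readings are tempting, and the documents do not support them:

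- **That the site check is confined to baseline mix.** SAP 11 names no variables and lists Cox models for event times, so an outcome check is permitted. Two of the mock table's columns, adjunct use and technique, are treatment choices rather than baseline features. What can be said is that no endpoint is specified.
- **That ±2% fails.** It fails only under assumed inputs. With 100 equal sites it survives ICC 0.01 and 0.02. In the less favourable layouts it is exceeded by 0.01 point at ICC 0.02. An ICC of 0.05 is also a strong assumption at this rate: it implies a between-site SD of √(0.05 × 0.083 × 0.917) = 6.2 points around a mean of 8.3%.
- **That combining small sites ("Any sites containing fewer than ten subjects will be aggregated in this analysis") spoils the check.** In a simulation with 600 registries per scenario at ICC 0.05, the power of a heterogeneity test was 0.76 with all sites separate and 0.73 with small sites merged at CV 0.5, and 0.68 and 0.82 at CV 1. There is no consistent loss, so the rule is not a defect here.

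A further caution concerns SAEs. At 1.7%, about 17 events are expected (0.017 × 1000), too few to estimate a between-site SD usefully. In simulated registries of 100 sites of 10 (150 runs per ICC), a random-intercept model put that SD at essentially zero in 47% of runs at a true ICC of 0.01 and in 24% at 0.02.

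**Conclusion.** The point holds as a low-severity improvement. Every specified binary interval, and the precision in SAP 2, assumes independence. Nothing in the plan would bring between-site outcome variation into an interval or lead anyone to act on it.

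How much this matters cannot be settled from the documents, which give neither an ICC nor a distribution of site sizes. Over the assumed ICC range of 0.01 to 0.05, the retreatment half-width grows by between 0.08 point (1.79 − 1.71) and 0.68 point (2.39 − 1.71). The ±2% statement is therefore conditional rather than wrong. Because 100 sites is a ceiling, fewer sites or uneven enrolment would lower the ICC at which it stops holding. The SAE precision is less exposed.

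**What to change.** 1. **SAP 8.1 and 10.1:** keep the binomial interval and add, as a sensitivity analysis, a 95% interval with site as the cluster (intercept-only GEE or a survey-type proportion). Do this for retreatment and for procedural SAE, the latter with a note that events are sparse.
2. **SAP 11 and its mock table:** name retreatment and procedural SAE and show both rates by site. Report a between-site SD for retreatment only. State that the clustered interval is to be read beside the binomial one whatever the check shows.
3. **SAP 2:** say that ±2% assumes independent subjects, and give the half-width over a stated ICC range, labelled as an assumption.

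This needs no new data, only a few lines of SAP text and standard SAS procedures. The cost is slightly wider sensitivity intervals and a little more programming. If sites turn out to be homogeneous, the two intervals will nearly agree, and that agreement will itself support pooling.
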